6. GENERAL ANALYSIS DEFINITIONS

6.1 TREATMENT(S)

For basic study information on the treatment to be administered, assignment to treatment, and selection of dose, cf. Section 4 of the CTP.

The study phases are defined relative to randomized dose at Day 1 as below:

Table 6.1: 1 Flow chart of analysis phases of the study according to randomized treatment

Study analysis phase	Description	Start (included)	End (included)
Screening phase	Screening	Earliest of (Date of informed consent, first screening procedure)	Date/time of start of the first study dose minus 1 minute.
Loading treatment phase	On-treatment period	Date/time of start of the first study loading dose (Day 1)	Earlier of: i) Date/time of start of the first maintenance dose minus 1 minute; or, ii) Date of end of last loading dose + 112 days at 11:59 p.m. if patient early discontinued study treatment before the first maintenance dose
Maintenance treatment phase (primary analysis at week 12)		Date/time of start of the first study maintenance dose (if applicable)	Earlier of : i) Date/time of start of the first dose in the extension trial 1368.67; or, ii) Date of end of last maintenance dose + 112 days at 11:59 p.m, iii) cut-off date for primary analysis.
Follow-up phase ¹ (if applicable)	Off-treatment period (if applicable)	Date of end of last study dose + 113 days at 0:00 a.m.	Latest of: i) Date of EOS visit; ii) last contact date on trial termination page at 11:59 p.m. iii) Date/time of start of first dose in the extension trial 1368.67;

Dates are defined individually per patient. If more than one date is associated with a specific visit, measurements associated with a specific date are assigned to a study analysis phase according to the rules specified in the table. An analysis phase will not extend beyond the start date of the following phase.

¹ The off-treatment period (i.e. Follow-up phase) only exists if the date of EoS visit or the last contact date is after the date of end of last administration + 112 days.

Treatment groups for the analysis phases according to the randomized/actual treatment on Day 1 (see [Table 6.1: 1](#)) will be labelled as follows:

Proprietary confidential information © 2021 Boehringer Ingelheim International GmbH or one or more of its affiliated companies

- **"Placebo"** (i.e. randomized to receive /actual received Placebo)
- **"Speso"** (i.e. randomized to receive /actual received Spesolimab)
- **"Overall Total"**(across treatments), where appropriate.

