7. PLANNED ANALYSIS

The following analyses of this trial protocol are planned:

Primary Analysis

The primary analysis will be performed once all patients have either 1) completed the 12 weeks treatment period or 2) have reached the 12 weeks after starting of treatment if early discontinued the trial treatment; for this assessment a first database lock (before the final database lock) will be performed.

The primary analysis will be performed by the sponsor. The project and trial team members will be un-blinded for treatment information and this analysis.

Note that biomarker data may be reported in a separate biomarker report at this time. If applicable, details of these analyses will be provided in a separate Biomarker Statistical Analysis Plan.

Final analysis

Final trial analysis will be performed once all randomized patients have completed the trial; at that time point, a final database lock will be done.

If separate primary analysis and final analysis, comprehensive analysis will be performed in the primary analysis. All data up to the cut-off date will be included for analysis. In final analysis, only concomitant medication/therapy and safety listings will be provided for these ongoing patients before trial completion at the time of database lock for primary analysis. A final clinical trial report will be written for all data from primary analysis and final analysis.

The primary analysis and final analysis may be performed as a single analysis (at the time of trial completion), if insufficient time interval between the two planned analysis and agreement by the trial team not to perform two separate analyses before the time of the primary analysis. For example, majority of patients enter the extension study and no patient is ongoing under REP at time of DBL of primary analysis.

The decision will be described and documented in final CTR.

General Remarks

The format of the listings and tables will follow the BI guideline "Standards for Reporting of Clinical Trials and Project Summaries " (*BI-KMED-BDS-HTG-0045*) ([10](#)) and those generated for PK are based on 001-MCS-36-472 ([5](#)).

The individual values of all patients will be listed. Listings will generally be sorted by country, center number, patient number and visit (if visit is applicable in the respective listing). AE listings will be sorted by assigned treatment (see [Section 7.8.1](#) below for details). The listings will be contained in Appendix 16.2 (SDL) of the CTR.

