7.8 SAFETY ANALYSIS

All safety analyses will be performed on the safety analysis set.

All safety analyses will be performed following BI standards. No hypothesis testing is planned. OC-IR and OR methods will be used for safety reporting. All safety analysis will be performed for on-treatment period.

AE and possibly clinically significant laboratory abnormalities will be analyzed under OR (as defined in [Section 6.6.3](#)); the safety data by visit, i.e., laboratory, vital signs and local tolerability, will be analysed under OC-IR (as defined in [Section 6.6.3](#)).

As the onset time of an AE will not be collected in the trial, any AE which occurs on the same day as a treatment dose will be assigned to the “post treatment”. For safety assessments by visits, if time is not collected, data on the same day of a treatment dose will be treated to be “prior treatment” except for scheduled local tolerability and post-dose vital signs assessments.

Off-treatment data will be listed only.

Additional analyses on AE will be also included:

AE within loading stage

Proprietary confidential information © 2021 Boehringer Ingelheim International GmbH or one or more of its affiliated companies
For AE, the additional safety tables for loading dose stage will be produced by grouping patients based on their loading doses (1200 mg, Placebo) using SAF. The outputs will include on-treatment data up to the first maintenance dose at or post week 4. If patients discontinued from treatment prior to receiving first maintenance dose, then the safety data up to the date of last loading dose + 112 days will be included.

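### If the primary and final analyses are run separately, adverse events after the cut-off but within 112 days of the last dose are listed but enter no frequency table, contrary to protocol 7.2.5

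*SAP*

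**What the plan says.** **Protocol.** Section 7.2.5 counts as treatment-emergent all adverse events from the start of treatment to the end of the residual effect period (REP), 16 weeks after the last dose. It requires frequency, severity and causality to be tabulated by system organ class and preferred term, with no exception for a data cut. Section 2.1.3 makes the occurrence of treatment-emergent adverse events a safety endpoint.

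**SAP section 7.** If the two analyses are separate, the comprehensive analysis is done at the primary analysis: "All data up to the cut-off date will be included for analysis". For patients still ongoing at that lock, "In final analysis, only concomitant medication/therapy and safety listings will be provided for these ongoing patients". The section adds: "A final clinical trial report will be written for all data from primary analysis and final analysis".

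**SAP Table 6.1:1.** The maintenance phase ends at the earliest of the first extension dose, the last maintenance dose + 112 days, and "iii) cut-off date for primary analysis". The follow-up phase starts at "Date of end of last study dose + 113 days at 0:00 a.m". Footnote 1 says: "The off-treatment period (i.e. Follow-up phase) only exists if the date of EoS visit or the last contact date is after the date" of the last administration + 112 days. The loading row has no cut-off limb. It runs to "Date of end of last loading dose + 112 days at 11:59 p.m. if patient early discontinued" before the first maintenance dose.

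**SAP 6.7, 7.8, 7.8.1 and 8.** Adverse event frequency tables use on-treatment data, and off-treatment data are only listed. For the loading-stage tables, if a patient stops before maintenance, "then the safety data up to the date of last loading dose + 112 days will be included". Section 7.8.1 defines the maintenance period for adverse events as the maintenance phase plus the REP. Section 8 describes the REP as off-treatment.

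**The concern.** The protocol defines the observation window for the safety endpoint, and the SAP's separate-analyses path cuts that window short in the tables. An event in the later part of the REP meets the protocol definition and is collected and listed. It is missing from the tables of treatment-emergent, serious, special-interest and drug-related events.

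The patients exposed are those who do not roll over, including early discontinuers sent into the 16-week safety follow-up. Adverse events are among the protocol's reasons for stopping treatment (3.3.4.1).

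The condition is realistic. The SAP's example of when to combine the analyses is that most patients enter the extension and none is still in the REP at the primary lock. By that example, separate analyses are likeliest when some patients are still in the REP, which is when events can be lost from the tables.

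The trial and project teams are unblinded at the first lock, so any table added afterwards would be chosen with treatment known.

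**Working it through.** The plan gives no figure for this point, so there is none to reproduce beyond 16 × 7 = 112 days, which agrees between protocol 7.2.5 and Table 6.1:1.

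**Step 1: does any text schedule a later table?**
- SAP 7 names listings only for the final analysis.
- The final report covers all data (SAP 7; protocol 8.6), but neither sentence provides updated frequency tables.
- SAP 7.8.1 adds the REP to the maintenance phase, which agrees with the protocol, but it names no rerun at final lock.
- SAP section 3 says the document fully specifies the analyses, so unstated tables should not be presumed.
- Read literally, Table 6.1:1 leaves the days from the cut-off to last maintenance dose + 112 in no phase. The cut-off limb may be meant only as the primary-analysis data cut, since its row is labelled for that analysis. The listings-only rule in SAP 7 produces the omission either way.

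**Step 2: inputs for the size**
- Maintenance doses on Days 29, 43, 57 and 71; end of treatment on Day 85; loading doses on Days 1, 8 and 15 (protocol flowchart).
- Assumption: the cut-off falls *c* days after Day 85 of the last-randomised patient. The SAP gives no date; section 8 ties data release to that patient's end-of-treatment visit plus cleaning.
- *d* = day of last maintenance dose; *u* = days by which a patient was randomised before the last one.

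Untabulated REP days = max(0, *d* + 112 − 85 − *c* − *u*).

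With *u* = 0:

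| Last dose (*d*) | REP ends (*d* + 112) | *c* = 0 | *c* = 14 | *c* = 28 | *c* = 56 |
|---|---|---|---|---|---|
| Day 29 | Day 141 | 56 (50%) | 42 | 28 | 0 |
| Day 43 | Day 155 | 70 (62.5%) | 56 | 42 | 14 |
| Day 57 | Day 169 | 84 (75%) | 70 | 56 | 28 |
| Day 71 | Day 183 | 98 (87.5%) | 84 | 70 | 42 |

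For example, *d* = 71 and *c* = 0 gives 71 + 112 − 85 = 98, and 98/112 = 87.5%. With the ±3-day windows at Weeks 10 and 12, the gap from last dose to end of treatment is 8 to 20 days, so the 98 becomes 92 to 104. Each day of earlier randomisation removes one day, so a completer randomised 98 or more days before the last patient loses nothing when *c* = 0.

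**Step 3: follow-up visits.** Protocol 3.1 places them at last dose + 56 and + 112 days:
- Day 29: Days 85 and 141
- Day 43: Days 99 and 155
- Day 57: Days 113 and 169
- Day 71: Days 127 and 183

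For completers, protocol 6.2.3 instead gives Weeks 20 and 28, and SAP Table 6.7:1 gives Days 141 and 197. On either schedule, both visits of a completer fall after Day 85.

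**Step 4: patients who stop during loading.** SAP 7.8 counts events to Day 1 + 112 = 113, Day 8 + 112 = 120 or Day 15 + 112 = 127. That is 28, 35 or 42 days past Day 85. SAP 7, read alone, would tabulate none of those later days, so the two sections conflict.

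**Step 5: effect on a frequency.** With planned arms of 30 and 15, one patient is 1/30 = 3.3% or 1/15 = 6.7%. The registry table in SAP 7.8.1 shows preferred terms above 5%, a threshold crossed by 1 of 15 or by 2 of 30 (6.7%).

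**The case against.** The strongest reply is that one loosely worded sentence carries the point. Section 7.8.1 counts the REP, the final report is to cover all data, and safety analyses follow internal sponsor standards that are not available here and might require tables to be rerun. Protocol 7.2.5 does not say at which lock the tables are made, and protocol 7.2 leaves detail to the SAP. On this view the SAP merely omits to say that the tables are updated.

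That does not succeed. SAP 7 states a restriction, not a silence: it limits the final output to listings. None of the other texts schedules a table after the cut-off, and an unseen standard cannot be assumed to override an explicit restriction.

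A second objection is about scope. The rule in SAP 7 is not confined to patients who reached maintenance, so it also catches those who stop during loading. That is right as a reading of SAP 7, but Table 6.1:1 and SAP 7.8 say otherwise for them. Their case is a conflict to reconcile, and it widens the point.

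A third is that the day counts are ceilings for one hypothetical patient, that the number affected may be zero, and that 3.3 or 6.7 points is what any single patient contributes in arms of this size. All of that stands. So does the reply that listings let a reader count late events, that a data monitoring committee reviews unblinded safety data, and that efficacy is untouched. These limit the severity but do not remove the departure from the protocol.

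**Conclusion.** The concern holds. On the separate-analyses path, the SAP as written leaves the treatment-emergent event endpoint and the related frequency tables incomplete against protocol 7.2.5.

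The clear loss concerns patients who received a maintenance dose, did not enter the extension and were within 112 days of their last dose at the cut-off. For patients who stopped during loading the SAP contradicts itself.

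The size rests on an assumed cut-off. It ranges from no days to 98 of 112 at the nominal visit days. How many patients are affected cannot be derived, because the documents give no roll-over rate or accrual period.

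This should be fixed, but it is not critical: the path is optional, safety is descriptive, and events are collected and listed. Confidence is medium because the internal standard on adverse event summaries could not be seen.

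**What to change.** - In SAP 7, replace the listings-only final analysis with a rerun at final lock of the treatment-emergent, serious, special-interest, drug-related and registry adverse event tables. Count events to the earlier of the first extension dose and the last dose, loading or maintenance, + 112 days. This also reconciles SAP 7 with SAP 7.8 for patients who stop during loading.
- State that the cut-off limb in Table 6.1:1 applies only to the primary-analysis data cut, and label the tables from that cut as data to the cut-off.
- Correct the description of the REP as off-treatment in SAP 8 to match Table 6.1:1 and protocol 7.2.5. This is a wording inconsistency, but it should go because SAP 7.8 sends off-treatment data to listings only.

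The change should be made before the first lock, while the team is still blinded. It costs a few lines of SAP text and a rerun of existing programs, with no new data. A single analysis at trial completion, which both documents already allow, would also avoid the loss.

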7.1 DEMOGRAPHIC AND OTHER BASELINE CHARACTERISTICS

Only descriptive statistics are planned for this section of the CTR.

Descriptive statistics will be presented by treatment for demographic parameters and baseline characteristics, based on the RS.

For the continuous variables described below, the following categories will be defined in [Table 7.1: 1](#), and presented according to the number and percentage of patients in each category:

Proprietary confidential information © 2021 Boehringer Ingelheim International GmbH or one or more of its affiliated companies
Table 7.1: 1 Categories for summary of continuous variables

Variable	Categories
Age	< 30 years 30 to < 65 years ≥ 65 years
Weight	≤60 kg >60 to ≤90 kg >90 kg
BMI	< 25 kg/m ² 25 to < 30 kg/m ² ≥ 30 kg/m ²
Time since first diagnosis	≤ 1 year > 1 to ≤ 5 year > 5 to ≤ 10 years > 10 years

7.2 CONCOMITANT DISEASES AND MEDICATION

Only descriptive statistics are planned for this section of the report. Analyses of concomitant diseases and medication will be based on the RS.

Concomitant diseases (i.e. baseline conditions) and concomitant non-drug therapies will be coded according to the most recent version of MedDRA. Concomitant medications will be coded according to the most recent version of the World Health Organisation – Drug Dictionary.

Concomitant diseases which are present at start of the study will be descriptively summarized by treatment.

A medication/non-drug therapy will be considered concomitant to treatment, if it

- is ongoing at the start of randomized trial treatment or
- starts within the on-treatment period (see [Section 6.1](#) for a definition of study analysis phases).

A medication/non-drug therapy will be considered as prior medication/non-drug therapy, if the end date of the medication/therapy is at any time prior to the start of randomized trial treatment.

Concomitant medication use (excluding rescue therapy) will be summarized with frequency and percentage of patients by preferred name. Summaries will be presented for

- concomitant medication starting any time prior to Day 1 (the day of start of trial treatment)
- concomitant medication starting any time during the on-treatment period (cf. [Section 6.1](#))

Proprietary confidential information © 2021 Boehringer Ingelheim International GmbH or one or more of its affiliated companies
Concomitant use of non-drug therapies (excluding rescue therapy) taken any time during the on-treatment period (cf. [Section 6.1](#)) will be summarized with frequency and percentage. Summaries will be presented for

- concomitant non-drug therapies starting any time prior to Day 1 (the day of start of trial treatment)
- concomitant non-drug therapies starting any time during the on-treatment period (cf. [Section 6.1](#)).

The frequency and percentage of patients with historical medication for HS will be displayed, including presentation by type of historical medication (preferred name), and by reason for discontinuation.

Use of rescue therapy will be summarized separately (see [Section 7.6.3](#)).

7.3 TREATMENT COMPLIANCE

Treatment compliance (see [Section 5.4.4](#) for the definition and calculation) will be summarized for the SAF using descriptive statistics (N, mean, SD, minimum, median, maximum). The number and percentage of patients with the following overall compliance categories will be presented:

- "< 80% of planned",
- "80 to 120% of planned" and
- "> 120% of planned".

7.4 PRIMARY ENDPOINT(S)

7.4.1 Primary analysis of the primary endpoint(s)

The primary analysis will implement the Hybrid strategy (EC-H) of handling intercurrent event defined in Section 5.4.6. Any data collected after the intercurrent event will be censored for the timepoint afterwards, i.e., only data prior to the ICE will be considered.

For the primary endpoint analysis, a restricted maximum likelihood (REML) based approach using a mixed model with repeated measurements (MMRM) is calculated to compare the adjusted relevant difference between the two arms.

MMRM analysis

The % change in total abscess and inflammatory nodule count from baseline (Visit 2), at Visits 3, 4, 5, 6, 7, 8 and 9 (Weeks 1, 2, 4, 6, 8, 10 and 12) will be evaluated using an MMRM accounting for the following sources of variation: fixed, categorical effects of treatment at each visit, the effect of stratum (stratification according to TNFi-naive population vs. TNFi-failure population) and the fixed continuous effects of baseline at each visit. The unstructured covariance structure will be used to model the within patient measurements. To estimate denominator degrees of freedom the Kenward-Roger approximation will be used.

In the event of model non-convergence, the methods described in [Section 10.2](#) will be utilized to resolve this.

SAS code for MMRM:

The following SAS code will be used to calculate the MMRM.

```
PROC MIXED DATA=alldat cl method=reml;  
  CLASS visit trt stratum subject;  
  MODEL ept = stratum visit*trt base*visit / ddfm=kr s CL;  
  REPEATED visit / subject= subject type=un r rcorr;  
  LSMEANS visit*trt / pdiff=all om cl alpha=0.05 slice=visit;  
RUN;
```

Results of the MMRM (N, mean, SE and 95% CI per dose group and timepoint) will be presented in tables and displayed graphically.

7.4.2 Sensitivity analysis, subgroup analysis, exploratory analysis of the primary endpoint(s)

Sensitivity analysis

As one sensitivity analysis for the primary endpoint, the observed data will be augmented with historical data. The 1368.52 placebo group will be combined with prior historical data for the placebo group from Humira Pioneer I and Pioneer II trials to derive the respective posterior distribution of the primary endpoint. A comparable population according to inclusion criteria in the current trial is obtained by trimming the historical data to patients with baseline total AN count no less than 5 and baseline total draining fistula count no larger than 20. A meta-analytic predictive (MAP) prior will be derived from the trimmed data. Similarly, the observed data of spesolimab group will be combined with a non-informative prior to derive the respective posterior distribution for spesolimab treatment. These posterior distributions will be used to evaluate the posterior treatment difference in primary endpoint between spesolimab and placebo. The posterior median and 95% credible intervals will be reported.

Furthermore, as the historical placebo data is from TNFi-naïve population, an additional sensitivity analysis will only consider the combination of the historical data with the observed data from TNFi-naïve patients in the placebo arm of the current study to derive the respective posterior distribution. The observed data from TNFi-failure patients in the placebo arm of the current study will be combined with a non-informative prior to derive the corresponding posterior distribution. The information from the strata will be weighted per sample size to obtain an overall estimate.

The MAP prior derivations for placebo arm obtained from Humira Pioneer I and Pioneer II trials, as well as posterior distribution for the treatment difference will be implemented following [Section 10.3.1](#).

In addition, the following sensitivity analysis for MMRM may be done:

- Sensitivity analyses utilizing MMRM model on different patients sets (such as the PPS)

Supplementary analysis

Proprietary confidential information © 2021 Boehringer Ingelheim International GmbH or one or more of its affiliated companies
The analysis based on supplementary strategy (EC-S) of handling intercurrent event defined in [Section 5.4.5](#) may be done if the interested event occurs. Any data collected after the intercurrent event will be censored for the timepoint afterwards.

Subgroup analysis

Subgroup analysis will use similar MMRM model as described for primary analysis of primary endpoint. A single MMRM model will be fitted involving all terms from the primary analysis model except replacing the treatment-by-visit term by the treatment-by-subgroup-by-visit term. Considering the exploratory nature of the study with small sample size, no test will be carried out to compare the treatment effect between spesolimab and placebo within subpopulation. The variables used for subgroup analysis is defined in [Section 6.4](#). If the model cannot converge, the level with smallest sample size will be excluded.

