- A sensitivity analysis utilizing the PPS to evaluate the impact on treatment outcomes of patients who may have relevant deviations from the conduct described in the CTP;
- The effect of stratum (TNFi-naive population versus TNFi-failure population) on the primary endpoint will be descriptively displayed via subgroup assessments.

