7.4 RANDOMIZATION

BI will arrange for the randomization and the packaging and labelling of trial medication. The randomization list will be generated using a validated system, which involves a pseudorandom number generator so that the resulting treatment will be both reproducible and

nonpredictable. The block size will be documented in the Clinical Trial Report. Access to the codes will be controlled and documented.

Stratification of the randomization will be performed for TNFi-naive population versus TNFi-failure population. Approximately 33 patients from TNFi-naive population and 12 patients from TNFi-failure population are planned to be randomized. Once either subpopulation has recruited the planned number of patients, the screening of that subpopulation may be considered to be closed.

Within each stratum, patients will be randomized in a 2:1 randomization ratio to receive Sepsolimab vs placebo. The randomization will be done in blocks to achieve balanced allocation.

The process of randomization is done via an IRT.

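### If the subgroup MMRM does not converge, the SAP's fallback would, at the planned sizes, drop the TNFi-failure level from that model and name no substitute summary

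*SAP*

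**What the plan says.** Protocol 7.4 sets up the strata: "Stratification of the randomization will be performed for TNFi-naive population versus TNFi-failure population". It gives the planned numbers, "Approximately 33 patients from TNFi-naive population and 12 patients from TNFi-failure population are planned to be randomized", and the allocation: "Within each stratum, patients will be randomized in a 2:1 randomization ratio".

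Among the secondary analyses of the primary endpoint, Protocol 7.2.2 lists: "The effect of stratum (TNFi-naive population versus TNFi-failure population) on the primary endpoint will be descriptively displayed via subgroup assessments".

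SAP 7.4.2 describes subgroup analysis as a single MMRM with all the terms of the primary model, "except replacing the treatment-by-visit term by the treatment-by-subgroup-by-visit term". It adds "The variables used for subgroup analysis is defined in" Section 6.4. No test of the treatment effect within a subgroup is planned. The paragraph ends: "If the model cannot converge, the level with smallest sample size will be excluded".

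For the primary model, SAP 7.4.1 takes a different route: "In the event of model non-convergence, the methods described in" Section 10.2 are used. The subgroup paragraph does not cite Section 10.2. Sections 6.4 and 10.2 are both missing from the public copy, and that is not held against the plan.

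SAP Table 6.3:1 attaches the subgroup footnote, for the primary endpoint, only to the EC-H-MMRM analysis. The observed-case displays (OC and OC-IR) are marked as descriptive and not as subgroup analyses.

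**The concern.** A rule that drops the smallest level can be reasonable for a factor with several levels, because a comparison still remains. For a two-level factor it leaves one level and nothing to set beside it. TNFi stratum has two levels. It is the only factor the randomization was stratified on, and the protocol says its effect on the primary endpoint will be shown.

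The remedy also does not match the likely difficulty. When an MMRM with an unstructured covariance fails to converge, the usual suspect is the covariance. Removing a level of a fixed effect does not shorten that matrix. It only takes away patients who inform it.

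At stake is a descriptive result for patients who failed a TNF inhibitor, a group enrolled by design, which a numerical failure could remove.

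**Working it through.** **Inputs.** Strata of 33 and 12, allocated 2:1 within each (Protocol 7.4). SD 45 points per arm; expected reductions of 62% and 20%; decision threshold 30 points; no missing data assumed in the sizing (Protocol 7.5). Seven post-baseline visits, unstructured covariance, and baseline-by-visit, treatment-by-visit and stratum terms (SAP 7.4.1).

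**Check of the design inputs.** With 30 and 15 patients:

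- SE = 45 × √(1/30 + 1/15) = 14.23 points.
- P(observed difference ≥ 30) = Φ((42 − 30)/14.23) = 80.05%.

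Protocol Table 7.5:1 gives 80.1%. A gamma simulation of 40,000 runs, taking 100 plus the percent change as gamma with the stated mean and SD, gives 79.95%. The inputs are therefore read as intended.

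**Which level the rule removes.** The smaller planned stratum is TNFi-failure. Split 2:1, it has 8 and 4 patients; TNFi-naive has 22 and 11. The share leaving the subgroup model is 12/45 = 26.7%.

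**What the rule does to the model**, with stratum as the subgroup variable:

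| | Both levels | TNFi-naive only |
|---|---|---|
| Patients | 45 | 33 |
| Treatment-by-subgroup-by-visit means | 2 × 2 × 7 = 28 | 2 × 7 = 14 |
| Baseline-by-visit slopes | 7 | 7 |
| Fixed effects in total | 35 | 21 |
| Covariance parameters, 7 × 8/2 | 28 | 28 |
| Residual df per visit, complete data | 45 − 5 = 40 | 33 − 3 = 30 |

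The separate stratum term is redundant when stratum is the subgroup, so it is not counted. The covariance keeps its 28 parameters and has fewer patients behind it.

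**What precision is at stake.** For a single visit, unadjusted and with complete data, SE = 45 × √(1/n₁ + 1/n₂):

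- TNFi-failure, 8 vs 4: SE 27.6; 95% half-width 1.96 × 27.6 = 54 points, or 61 points with t on 10 df.
- TNFi-naive, 22 vs 11: SE 16.6; half-width about 33 points (normal) or 34 points (t on 31 df).

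Under the rule the first line disappears and only the second is reported.

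**Whether another planned output fills the gap.** For the primary endpoint by subgroup, Table 6.3:1 marks only the MMRM that would lose the level. The continuous secondary endpoints have the same marking, and SAP 7.5.2 plans subgroup analysis for them. The binary secondary endpoints have a subgroup analysis under NRI, which does not depend on the MMRM. No visible text calls for observed means by stratum if the level is excluded.

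**The case against.** Several counter-arguments carry weight.

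- **The subgroup list is hidden.** That stratum is on it is an inference from Protocol 7.2.2. The rule may have been written for multi-level variables with a sparse level. This stands as a limit, but the visible sentence makes no exception for a two-level factor.
- **Section 10.2 may come first.** SAP 7.4.2 calls the subgroup model similar to the primary one, so exclusion could be a last resort after the Section 10.2 steps. A reader might infer that those steps are bypassed; the text does not establish that. It leaves the order open, which is itself worth settling before unblinding.
- **Non-convergence may be unlikely.** A reader might infer from 28 cell means and 28 covariance parameters in 45 patients that failure is to be expected. The count does not show this. With complete data and stratum as the subgroup, each visit has the same regressors, so the REML covariance has a closed form on about 40 residual df for a 7 × 7 matrix. Missing visits and values censored after rescue make the fit iterative, so failure cannot be ruled out, but no probability can be read from the documents.
- **TNFi-failure patients are not lost to the trial.** A reader might infer that the trial could end with nothing on this group. That is too strong. They stay in the primary MMRM. If stratum is in Section 6.4, binary endpoints such as HiSCR would still be shown by stratum. The additional Bayesian sensitivity analysis in SAP 7.4.2 treats TNFi-failure placebo patients separately, and individual values are listed.
- **No planned contrast is lost.** The visible SAP specifies no comparison between strata and no test within them. The protocol promises only a description.
- **The estimate is weak.** A half-width of 54 to 61 points against an assumed effect of 42 supports no decision. That is true, but an imprecise description, labelled as such, is still what the protocol undertook to show.

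**Conclusion.** The point holds as a minor, conditional weakness in a fallback rule. If the subgroup MMRM by TNFi stratum fails to converge and the sentence is applied as written, about 12 of 45 patients (27%) leave that model. The by-stratum display of the primary endpoint is then reduced to TNFi-naive patients, with no replacement in the visible SAP. The rule also leaves the covariance as complex as before and reduces the patients available to estimate it.

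This rests on three assumptions: that stratum is among the Section 6.4 variables; that actual stratum sizes resemble the approximate planned ones, since the rule acts on the numbers observed; and that Section 10.2 does not already govern the subgroup model. The effect is confined to the subgroup MMRMs for the primary and continuous secondary endpoints. The primary result is not affected, and no claim is made that non-convergence is likely.

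**What to change.** Replace the last sentence of the subgroup paragraph in SAP 7.4.2 with wording such as: *If the subgroup model does not converge, all levels are kept and the non-convergence steps used for the primary model (Section 10.2), including a simpler covariance structure, are applied first; if it still fails, observed means and SDs by arm, visit and subgroup level are presented.*

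This settles the order relative to Section 10.2, acts on the covariance and not on the patients, and secures the display promised in Protocol 7.2.2. The authors should confirm that Section 10.2 does contain a simpler covariance step, and make the change before treatment codes are released.

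The cost is one sentence, possibly one extra table, and no new data. The downside is a TNFi-failure estimate that is easily over-read, so the output should be labelled descriptive and show the patient numbers per cell.
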